4.0	[name], [name], [name]	[name]	14DEC2021	Clarification of data collection procedures prior to initiation of intraocular treatment for DR or DME at annual and non-annual visits. Clarified that one dose of study drug is one pill. Modified eligibility criteria for eGFR from ≥ 60 to ≥ 45 at screening, with eGFR 45 to <60 starting on the reduced dose. Modified eligibility to include participants with one study eye. Extended allowable window for lab draw at screening. Changed criteria for diabetic retinopathy worsening on photos from 3 or more steps on person scale to 2 or more steps on an eye scale. The unit of analysis for the primary outcome has been changed from a participant to a study eye; statistical methods have been updated accordingly. Added whether a participant has one or two study eyes as a randomization stratification factor.
4.1	[name]	[name]	20JUL2022	Updated FA transit eye instructions; revision to how renal function safety outcomes are defined; miscellaneous revisions to the statistical methods; minor typos and formatting corrections. Since changes are minor, sign-off not required by study personnel.
5.0	[name]	[name]	13APR2023	Expanded allowable windows for select screening procedures; pregnancy test to be completed at randomization visit in-clinic if >30 days since screening; updated visual acuity, liver, and glaucoma eligibility criteria; truncation of continuous outcomes updated to be truncated to ± 3 standard deviations
6.0	[name], [name]	[name]	18OCT2023	Sample size reduced to 560; follow-up visits added through up to 6 years for new participants, with option to extend for past 4 years for participants enrolled at time of amendment; procedures updated throughout for visits and phone calls beyond 48 months; Informed consent addendum process added for participants enrolled prior to protocol v6.0; replaced Unknown with 'Ongoing (Medically Stable)' as an AE outcome

TABLE OF CONTENTS

CHAPTER 1: BACKGROUND INFORMATION	20
1.1 Introduction.....	20
1.1.1 Diabetic Retinopathy Complications and Public Health Impact	20
1.1.2 Preventing DR Onset and Worsening	20
1.1.3 Limitations of Current Treatments for DR and DME.....	21
1.1.4 Rationale for Fenofibrate Therapy for DR Worsening	21
1.1.5 Ongoing Multicenter Studies Evaluating Fenofibrate and DR	23
1.2 Summary of Study Rationale.....	24
1.3 Rationale for Ancillary Components	25

11.1 Case Report Forms and Other Data Collection 82

11.2 Study Records Retention 82

11.3 Quality Assurance and Monitoring..... 82

11.4 Protocol Deviations..... 83

CHAPTER 12: ETHICS/PROTECTION OF HUMAN PARTICIPANTS..... 84

12.1 Ethical Standard..... 84

12.2 Institutional Review Boards..... 84

12.3 Informed Consent Process 84

12.3.1 Consent Procedures and Documentation 84

12.3.2 Participant and Data Confidentiality..... 85

12.3.3 Future Use of Stored Data..... 85

CHAPTER 13: REFERENCES..... 87

LIST OF ABBREVIATIONS

ABBREVIATION	DEFINITION
ACCORD	Action to Control Cardiovascular Risk in Diabetes
AMD	Age-Related Macular Degeneration
AE	Adverse Event
ALT	Alanine Transaminase
APTC	Antiplatelet Trialists' Collaboration
anti-VEGF	anti-Vascular Endothelial Growth Factor
AST	Aspartate Transaminase
CBC	Complete Blood Count
CGM	Continuous Glucose Monitor
CRF	Case Report Form
CI-DME	Center-Involved Diabetic Macular Edema
CFR	Code of Federal Regulations
CI	Confidence Interval
CK	Creatine Kinase
DSMC	Data and Safety Monitoring Committee
DVT	Deep Vein Thrombosis
DCCT	Diabetes Control and Complications Trial
DME	Diabetic Macular Edema
DR	Diabetic Retinopathy
ETDRS	Early Treatment Diabetic Retinopathy Study
E-ETDRS	Electronic ETDRS
EVA	Electronic Visual Acuity
eGFR	Estimated Glomerular Filtration Rate
FIELD	Fenofibrate Intervention and Event Lowering in Diabetes
FA	Fluorescein Angiography
FDA	Food and Drug Administration
GCP	Good Clinical Practice
HbA1c	Hemoglobin A1c
HDL	High Density Lipoproteins

ABBREVIATION	DEFINITION
ICGA	Indocyanine Green Angiography
IRB	Institutional Review Board
ITT	Intention-to-Treat
IOP	Intraocular Pressure
IND	Investigational New Drug
JCHR	Jaeb Center for Health Research
LFT	Liver Function Tests
LENS	Lowering Events in Non-proliferative Retinopathy in Scotland
NIH	National Institutes of Health
NPDR	Non-Proliferative Diabetic Retinopathy
NV	Neovascularization
NVD	Neovascularization of the Disc
NVE	Neovascularization Elsewhere
OCT	Optical Coherence Tomography
OCTA	Optical Coherence Tomography Angiography
PRP	Panretinal (Scatter) Photocoagulation
PPAR α	Peroxisome Proliferator-Activated Receptor α
PCP	Primary Care Provider
PDR	Proliferative Diabetic Retinopathy
PE	Pulmonary Embolus
RCT	Randomized Controlled Trial
RC	Reading Center
RR	Relative Risk
RNFL	Retinal Nerve Fiber Layer
RNA	Ribonucleic Acid
SAE	Serious Adverse Event
SD-OCT	Spectral Domain OCT
SD	Standard Deviation
SUSAR	Suspected Unexpected Serious Adverse Reaction
TIR	Time-In-Range
VA	Visual Acuity

ABBREVIATION	DEFINITION
VF	Visual Field

PROTOCOL SUMMARY

[figure not shown]
ITEM	DESCRIPTION
Title	A Randomized Clinical Trial Evaluating Fenofibrate for Prevention of Diabetic Retinopathy Worsening
Précis	
This randomized trial will evaluate the effect of fenofibrate compared with placebo for prevention of diabetic retinopathy (DR) worsening through at least 4 but up to 6 years of follow-up in eyes with mild to moderately severe non-proliferative DR (NPDR) and no CI-DME at baseline.
 
In addition to evaluating efficacy, this study aims to evaluate the feasibility of a model for ophthalmologists to prescribe or collaborate with a primary care provider such as an internist/endocrinologist to prescribe and monitor the drug safely. If this study demonstrates that fenofibrate is effective for reducing the onset of proliferative diabetic retinopathy (PDR) and the results are adopted by the community of retina specialists, a new strategy to prevent vision threatening complications of diabetes could be widely adopted. Widespread use of an oral agent effective at reducing worsening of DR would decrease the numbers of patients who undergo more invasive and much more expensive treatment for DR and who are consequently at risk for side effects that adversely affect visual function.
 
This study will also assess the relationship of glycemic variability, as measured by continuous glucose monitoring, with DR outcomes. Ancillary studies will characterize functional and structural outcomes in this cohort.

Investigational Drug	Fenofibrate (new indication)
Objectives	
The primary objective is to determine if fenofibrate is effective at preventing DR worsening in eyes with mild to moderately severe non-proliferative DR and no CI-DME at baseline.
 
Additional goals of the study are to 1) provide a model for ophthalmologists to prescribe or collaborate with a primary care provider to prescribe and monitor the drug safely, 2) disseminate standardized prescribing guidelines with the aim to encourage broader use, and 3) collect information on potential predictive biomarkers of DR progression via blood sampling, functional, and structural testing as well as glucose levels from CGM.

Study Design	Randomized, double-masked, placebo-controlled clinical trial

ITEM	DESCRIPTION
Number of Sites	Approximately 80
Endpoint	
Primary Efficacy Outcome:
 
Worsening of DR through 6 years (time-to-event composite outcome) defined as any of the following in a study eye (see details in Section 10.4.1):
 
 • 2 or more step worsening on ETDRS DR severity on fundus photographs. • Development of NV within the 7-modified ETDRS fields on fluorescein angiography. • Intraocular procedure undertaken to treat DR including PRP, intraocular anti-VEGF, corticosteroid, or vitrectomy. 
Key Safety Outcomes:
 
Myopathy, rhabdomyolysis, renal disease (eGFR decreased below 30, dialysis, or renal transplant), cholelithiasis, increased liver function tests (ALT or AST), low HDL, muscle pain or weakness, easy bruising or bleeding, death, APTC events

Population	
Key Inclusion Criteria
 
 • Age ≥ 18 years and < 80 years. • Type 1 or type 2 diabetes. • At least one eye with the following: 
 ○ Mild to moderately severe NPDR (defined by ETDRS DR severity level 35 to 47), confirmed by central Reading Center grading of fundus photographs. ○ Best-corrected E-ETDRS visual acuity letter score of ≥ 74 (approximate Snellen equivalent 20/32 or better). • If only one eye is eligible, the non-study eye must have at least microaneurysms only (DR severity level 20) 
Key Exclusion Criteria
 
Eye-level exclusion criteria (the eye is ineligible if any of the following is met):
 
 • Current CI-DME based on clinical exam or OCT central subfield thickness (CST) 
 ○ Zeiss Cirrus: CST ≥ 290 μm in women or ≥ 305 μm in men ○ Heidelberg Spectralis: CST ≥ 305 μm in women or ≥ 320 μm in men

ITEM	DESCRIPTION
	
 • Any prior treatment for DME or DR, other than focal/grid laser. If the eye has a history of focal/grid laser, it must be at least 12 months prior. • History of intraocular anti-VEGF or corticosteroid treatment within the prior year for any indication 
Participant-level exclusion criterion (the participant is ineligible if the following criterion is met):
 
 • Decreased renal function, defined as requiring dialysis or central laboratory eGFR value < 45 mL/min/1.73 m²
Sample Size	560 participants
Treatment Groups	Random assignment (1:1) to fenofibrate or placebo
Participant Duration	At least 4 but up to 6 years of follow-up for each randomized participant.
Protocol Overview/Synopsis	
 1. Informed consent will be obtained. 
 a. Participants enrolled after effective date of Protocol v6.0 will be in the study up to 6 years. b. Participants enrolled prior to Protocol v6.0 will be followed for at least 4 years, and will be asked to continue through up to 6 years if the outcome has not yet been met. Consent will be collected via an ICF addendum. 2. Study eligibility will be assessed by the site. 3. Potentially eligible participants will complete a Screening visit after which: 
 a. Eligibility will be confirmed via lab results and RC grading of DR severity level. b. Approval to participate in the study will be obtained from the participant's health care provider responsible for primary systemic management (e.g., endocrinologist or primary care provider). 4. Eligible participants will be randomly assigned 1:1 to fenofibrate or placebo. 5. Participants will return for a follow-up visit at 3 months, 6 months, and every 6 months thereafter through at least 4 years. Participants meeting criteria for additional follow-up after 4 years could have visits annually through 6 years, depending on the timing of their enrollment into the study. 6. Phone calls to the participant will be made at 3-month intervals in-between 6-month interval visits, starting after the 6-month visit, and every 3 months after the 48-month visit.

ITEM	DESCRIPTION
	
7. Participation in the study will be considered completed upon completion of either:
 
 a. the 4-year (48-month) visit if the participant has met the definition of the primary efficacy outcome or does not consent to visits beyond 4 years b. OR the last completed visit approximately 4 years after the final study participant's enrollment. Participants will return for a final completion visit if their prior visit was more than 6 months before the completion of the trial. c. OR the 6-year (72-month) visit

SCHEMATIC OF STUDY DESIGN

* For participants who meet criteria for follow-up beyond 4 years; the last visit for each participant will depend on when the last enrolled participant completes their 4-year visit.

SCHEDULE OF STUDY VISITS AND PROCEDURES

In addition to the visits listed below, phone calls will be made from the site at 3-month intervals in between in-person visits, starting after the 6-month visit (months 9, 15, 21, 27, 33, 39, 45) and at months 51, 54, 57, 63, 66 and 69 following for participants enrolled through 6 years. All procedures will be performed on both eyes, unless otherwise indicated in the footnotes.

Visit	Screening Visit	Randomization Visit	3-Month Safety Visit	6-Month Visit	Annual Visits (12, 24, 36, 48-Months) *	18, 30, 42-Month Visits	60 and 72 Months, Completion Visit
Visit Window		<60 days from Screening	±2 weeks	±4 weeks	±8 weeks	±4 weeks	±8 weeks
Randomization		X					
Visual acuity ^a	X	X		X	X	X	X
OCT	X			X	X	X	X
Eye Exam ^b	X	X		X	X	X	X
Fundus Photography ^c	X				X		X
Fluorescein Angiography ^c	X				X		X
Blood Pressure	X	X	X	X	X		X
Urine sample for creatinine, albumin, and pregnancy test (if female of child-bearing potential)	X	Pregnancy test only (if > 30 days from screening) ^k	X	X	X	Pregnancy test only (Central Lab)	X
Whole blood sample for CBC and HbA1c ^d	X		CBC only	X	X		X
Serum sample for LFTs, serum creatinine, eGFR, CK, and lipid panels ^e	X		X	X	X		X
Safety assessment ^f			X	X	X	X	X
Assess Compliance with Study Drug Regimen			X	X	X	X	X
CGM Insertion ^g		X		X	X	X	X
Ancillary Components – the following tests will only be performed at select sites and/or on select participants							
OCT Angiography ⁱ		X		X		X	X
Humphrey Visual Field ^h		30-2 & 60-4		30-2	60-4	30-2	30-2 & 60-4
Contrast sensitivity ^j		X			X		X
Biomarker serum sample	X		X	X	X		X

JAEB CENTER FOR HEALTH RESEARCH

RNA sample	X		X	X	X		X
------------	---	--	---	---	---	--	---

*= If treatment with intraocular medication, PRP, or vitrectomy is initiated in a study eye at a non-annual or non-study visit, all annual visit ocular testing and all study ancillary components (OCTA, visual field, and contrast sensitivity) will be completed in the eye(s) to be treated. For testing that is to be performed pre-dilation, post-dilation testing will be accepted if the decision to treat is made after dilation.

a= Usual care vision acceptable at Screening Visit; otherwise, visual acuity testing includes protocol refraction at each visit followed by electronic-ETDRS testing using the Electronic Visual Acuity Tester that has been validated against 4-meter chart ETDRS testing.

b= Includes slit lamp exam (including assessment of lens), measurement of intraocular pressure, and dilated ophthalmoscopy.

c= Using the widest approach available (e.g. ultrawide field imaging device).

d= CBC = complete blood count; for HbA1c, central laboratory value preferred but value available from within the prior 3 months may be used if central lab sample cannot be analyzed. CBC only at 3-month visit.

e= LFTs = liver function tests; eGFR = estimated glomerular filtration rate; CK = creatine kinase; fasting required for lipid panels at screening and the 48, 60 & 72-month visits.

f= safety assessments include questions related to symptoms of myopathy/rhabdomyolysis or cholelithiasis.

g= a “masked” CGM sensor will be placed and worn for approximately 10 days. The CGM will then be mailed back to the Coordinating Center for processing of the data.

h= HVF 30-2 and 60-4 performed on both eyes at randomization and the 60 & 72 month visits.

30-2 on study eye(s) only at months 6, 18 & 30, and on non-study eye also at month 42.

60-4 on study eye(s) only at months 12, 24 & 36, and on non-study eye also at month 48.

i= OCTA is performed on the study eye(s) at all visits indicated, but is performed on the non-study eye also at randomization and the 42, 60, and 72-month visits.

j= Contrast Sensitivity is performed on the study eye(s) at all visits indicated, but is performed on the non-study eye also at randomization and the 48, 60 and 72-month visits.

k= At randomization, a pregnancy test must be completed at the site (for females who are premenopausal and are not surgically sterile) if randomization visit >30 days from screening. Pregnancy testing at all other visits must be performed by central lab.

Chapter 1: Background Information

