637 **2.3 Screening Procedures**

638 After informed consent has been signed, a potential participant will be evaluated for study
 639 eligibility through the elicitation of a medical history and performance of an ocular examination
 640 by study personnel to screen for exclusionary conditions.

641 Individuals who do not initially meet study eligibility requirements may be rescreened at a later
 642 date per investigator discretion.

643 All testing does not need to be completed on the same day provided it is within the windows
 644 specified below. The screening visit should be scheduled early in the day to accommodate fasting
 645 requirements for blood samples.

646 **2.3.1 Data Collection and Testing**

647 The following procedures are needed to confirm eligibility and/or serve as baseline measures for
 648 the randomized trial:

649 • If a procedure has been performed using the study technique and by study certified
 650 personnel as part of usual care, then it does not need to be repeated specifically for the
 651 study if it was performed within the defined time windows specified below.

652 • The testing procedures are detailed in the DRCR Retina Network procedures manuals. See
 653 Chapter 7 for which testing requires certified personnel.

654 • The fundus photographs and fluorescein angiograms will be promptly sent to the central
 655 reading center for grading and a participant cannot be randomized until reading center
 656 confirmation of eligibility has been received.

657 ○ Separately, automated grading may be done as an ancillary component to evaluate
 658 the accuracy of automated grading systems. However, those results will not be
 659 considered for eligibility.

660 • Screening procedures will last approximately 4 hours.

661 1. Self-reported demographics (date of birth, sex, race and ethnicity)

662 2. Medical history (pre-existing medical conditions, concomitant medications, as well as ocular
 663 diseases, surgeries, and treatment)

664 ➤ Medical history will be obtained by medical charts if available at the enrolling site;
 665 otherwise, it will be self-reported

666 3. Visual acuity using clinic’s usual care method or electronic-ETDRS visual acuity testing at 3
 667 meters using the Electronic Visual Acuity Tester in both eyes (*within 8 days of ocular*
 668 *examination*).

669 4. Spectral-domain OCT using Zeiss Cirrus or Heidelberg Spectralis in both eyes (*within 8 days*
 670 *of ocular examination*).

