 849 *or prior to 4 years, for the last enrolled participant, **or** for participants who only consent to stay*
 850 *enrolled in the trial through 48 months.*

851 ** *The end of the study will occur approximately 4 years after the last participant is enrolled. For*
 852 *participants in follow-up beyond 48 months, a final visit should be scheduled around the same*
 853 *projected timepoint if more than 6 months have passed since the participant's prior 48 or 60-*
 854 *month visit (irrespective of the target and allowable windows for the next scheduled visit).*
 855

856 The goal will be for all participants to complete all scheduled visits. However, participants who
 857 (because of unforeseen circumstances) are unable or unwilling to return for all follow-up visits
 858 will be permitted to return for key visits only as an alternative to withdrawal from the study. When
 859 a participant is placed into this status, missed visits will not be recorded as protocol deviations
 860 (since they would not be recorded as protocol deviations if the participant was dropped from the
 861 study).

862 Additional office visits may occur as needed.

863 **5.3.2 Procedures at Study Visits**

864 **3-Month Safety Visit**

865 *At the 3-month safety visit, only safety and compliance assessments will be conducted including:*

- 866 1. Measurement of blood pressure.
- 867 2. Blood draw (fasting *not* required) for:
 - 868 • LFTs, serum creatinine (used for eGFR), CK, and CBC
 - 869 • Biomarker serum and/or RNA sample (only for sites/participants who participate)
 - 870 ➤ *The central laboratory must be used – see study procedure manual for collection*
 - 871 *procedure.*
- 872 3. Urine sample for:
 - 873 • Creatinine and albumin Pregnancy test for all females who are premenopausal and are not
 - 874 surgically sterile
 - 875 ➤ *The central laboratory must be used – see study procedure manual for collection*
 - 876 *procedure.*
- 877 4. Safety assessment of symptoms of myopathy/rhabdomyolysis or cholelithiasis
- 878 5. Compliance assessment

879 880 **6-Month Interval Visits**

881 The following procedures will be performed at each *6-month interval* study visit.

- 882 1. E-ETDRS visual acuity testing in each eye (best corrected).
- 883
 - 884 • A protocol refraction in both eyes is required at all study visits.
- 885 2. Ocular exam on both eyes, including slit lamp examination, lens assessment, measurement of
- 886 intraocular pressure and dilated ophthalmoscopy

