 1037 endocrinologist. If any of the values necessitate further action according to the Dose Titration
 1038 Schedule in section 6.1.7 this will be communicated to the PCP by the site.

1039 **5.3.5 Phone Contacts**

1040 A phone contact will be completed by certified site personnel (investigator or coordinator) at the
 1041 following times:

Phone Call	Target Day/Week	Target Window (around Target Day/Week)	Allowable Window (around Target Day/Week)
9 Month	39 Weeks	±2 weeks	-4 weeks/+8 weeks
15 Month	65 Weeks	±2 weeks	-4 weeks/+8 weeks
21 Month	91 Weeks	±2 weeks	-4 weeks/+8 weeks
27 Month	117 Weeks	±2 weeks	-4 weeks/+8 weeks
33 Month	143 Weeks	±2 weeks	-4 weeks/+8 weeks
39 Month	169 Weeks	±2 weeks	-4 weeks/+8 weeks
45 Month	195 Weeks	±2 weeks	-4 weeks/+8 weeks
51 Month	221 Weeks	±2 weeks	-4 weeks/+8 weeks
54 Month*	234 Weeks	±2 weeks	-4 weeks/+8 weeks
57 Month	247 Weeks	±2 weeks	-4 weeks/+8 weeks
63 Month	273 Weeks	±2 weeks	-4 weeks/+8 weeks
66 Month*	286 Weeks	±2 weeks	-4 weeks/+8 weeks
69 Month	299 Weeks	±2 weeks	-4 weeks/+8 weeks

1042 *Phone calls are performed every 3 months following the year 4 and 5 visits for participants still
 1043 in follow-up, since in-person visits only occur annually

1044 The purpose of the phone contact will be to:

- 1045 ➤ Emphasize compliance with daily medication and answer any questions
- 1046 ➤ Assess symptoms of myopathy/rhabdomyolysis or cholelithiasis

1047 Additional phone contacts may be performed as needed. If the participant is in for an unscheduled
 1048 visit during the call window, the call procedures can be completed at that time.

1049 **5.4 Early Termination Visit**

1050 Study participants who request to withdraw will be asked to have a final closeout visit at which
 1051 the testing described for study visits will be performed.

1052 **5.5 Unscheduled Visits**

1053 Additional visits may occur as required for usual care of the study participant. Testing procedures
 1054 at unscheduled visits are at investigator discretion, provided DR or DME treatment is not planned
 1055 (see section 5.6 below).

1056 **5.6 Study Eye Treatment Initiation Visit**

1057 Prior to the first time administration of intraocular treatment for DR or DME in the study eye(s)
 1058 (e.g., anti-VEGF or corticosteroid intraocular injection, PRP, focal/grid laser, or vitrectomy),
 1059 participants will be asked to complete the ocular study procedures performed at an annual visit

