1702 Analyses for the CGM sub-study will be described in a separate statistical analysis plan. The
 1703 primary objective is to evaluate the relationship between glycemic parameters (e.g., time-in-range)
 1704 with DR progression.

1705 Analysis of ancillary study data involving biomarker samples, OCT angiography, Humphrey
 1706 visual fields, and contrast sensitivity also will be described in a separate statistical analysis plan.

1707 **10.9 Safety Analyses**

1708 All reportable adverse events in the safety analysis cohort will be tabulated by treatment group
 1709 according to Medical Dictionary for Regulatory Activities (MedDRA) term and summarized over
 1710 each MedDRA System Organ Class. In the unlikely event there is a delay in treatment initiation,
 1711 any events occurring between randomization and treatment initiation will be included in reported
 1712 event totals, but the number of such events will be specifically noted.

1713 The number and percentage of participants having a systemic adverse event occurring at least once
 1714 will be calculated for each reportable event. The following systemic adverse events will be
 1715 tabulated (precise definitions of each outcome will be specified in the statistical analysis plan):

- 1716 • Myopathy
- 1717 • Rhabdomyolysis
- 1718 • Change in renal function defined as any of the following:
 - 1719 ○ eGFR reduced from ≥ 60 to < 60
 - 1720 ○ eGFR reduced from ≥ 30 to < 30
 - 1721 ○ Dialysis
 - 1722 ○ Renal transplant
- 1723 • Increased liver function tests (ALT or AST)
- 1724 • Low HDL
- 1725 • Cholelithiasis
- 1726 • Muscle pain or weakness
- 1727 • Easy bruising or bleeding
- 1728 • Death
- 1729 • Cardiovascular and cerebrovascular events according to the Antiplatelet Trialists'
 1730 Collaboration:⁷¹
 - 1731 ○ Nonfatal myocardial infarction
 - 1732 ○ Nonfatal stroke (counted only if symptoms lasted at least 24 hours)

1733 ○ Death attributed to cardiac, cerebral, hemorrhagic, embolic, other vascular (does
1734 not need to be ischemic in origin), or unknown cause

1735 ○ At least one event (nonfatal myocardial infarction, nonfatal stroke, or death
1736 attributed to potential vascular or unknown cause)

1737 ● Hospitalization

1738 ● Serious systemic adverse event

1739 The following also will be tabulated by treatment group without formal statistical comparison:

1740 ● Number of adverse events

1741 ● Number of serious adverse events

1742 ● Number of hospitalizations

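### Easy bruising or bleeding is a named key safety outcome, but no listed safety question covers it, and the symptom questions have no baseline before the first pill

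*Protocol*

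**What the plan says.** The Endpoint entry of the Protocol Summary gives the key safety outcomes, ending with "muscle pain or weakness, easy bruising or bleeding, death, APTC events". Section 10.9 repeats the item "Easy bruising or bleeding" among the systemic adverse events, to be reported as the number and percentage of participants with at least one occurrence. It leaves the precise definition of each outcome to the SAP.

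The collection side is described in several places:

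- Schedule footnote f: "safety assessments include questions related to symptoms of myopathy/rhabdomyolysis or cholelithiasis".
- Section 5.3.2, 3-month visit, item 4: "Safety assessment of symptoms of myopathy/rhabdomyolysis or cholelithiasis". The 6-month interval visits, the year 1-4 annual visits and the year 5-6 visits carry the same list.
- Section 5.3.5, phone contacts: "Assess symptoms of myopathy/rhabdomyolysis or cholelithiasis".
- The schedule row "Safety assessment" is blank at Screening and at Randomization. Section 4.1 lists no symptom questions, and section 4.2 has the first pill taken at the site on the day of randomization.

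For baseline, section 2.3.1 item 2 collects pre-existing conditions and concomitant medications: "Medical history will be obtained by medical charts if available at the enrolling site", and by self-report otherwise. Section 9.1 records any condition present at screening. Exclusion 18 removes people with severe myalgia that led to stopping lipid-lowering treatment. Section 8.2.2 makes every adverse event reportable, by whatever route it comes to light.

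**The concern.** A symptom that is asked about repeatedly is usually reported more completely than one that is not. Here muscle and gallstone symptoms are prompted at every scheduled contact from month 3, while bruising or bleeding, which has the same rank in the synopsis, has no named prompt. A small or absent difference in bruising could then reflect thin collection rather than safety. That matters in a trial whose stated goals include a model for monitoring the drug safely and the spread of prescribing guidelines.

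The second matter is timing. The muscle questions are first asked about 13 weeks into treatment, and no answer to the same questions exists from before the first pill. A long-standing ache that first surfaces under questioning at month 3 is hard to tell from a new one. Neither gap can be closed at the analysis stage, because a definition written in the SAP cannot recover an answer that was never sought.

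**Working it through.** **Coverage, set side by side**

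| Symptom outcome | Named in the visit and phone questions? | Same question before first pill? |
|---|---|---|
| Muscle pain or weakness | Yes, through the myopathy/rhabdomyolysis symptoms | No |
| Cholelithiasis | Yes | No |
| Easy bruising or bleeding | No | No |

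**Number of prompted contacts to month 48.** Visits at months 3, 6, 12, 18, 24, 30, 36, 42 and 48 make 9. Calls at months 9, 15, 21, 27, 33, 39 and 45 make 7. The total is 9 + 7 = 16.

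**Effect of the two mechanisms.** The protocol states no expected rate, capture rate or power for these outcomes, so there is no figure to reproduce. What follows is illustration only. It assumes 280 per arm (section 10.3.2), two-sided 5%, error equal in the two arms, and assumed true new-onset rates of 5% (placebo) and 10% (fenofibrate). Power is the two-proportion normal approximation, Φ[(Δ − 1.96·SE₀)/SE₁], where SE₀ uses the pooled rate and SE₁ the separate rates.

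*(a) Under-capture (bruising or bleeding).* Observed rate = s × true rate, where s is the share of events captured. The ratio is (s × 10%)/(s × 5%) = 2.0 for any s. The difference is s × 5 points.

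| s | Observed rates | Risk ratio | Difference (points) | Power |
|---|---|---|---|---|
| 1.0 | 5% vs 10% | 2.0 | 5.0 | 61% |
| 0.8 | 4% vs 8% | 2.0 | 4.0 | 51% |
| 0.5 | 2.5% vs 5% | 2.0 | 2.5 | 34% |
| 0.3 | 1.5% vs 3% | 2.0 | 1.5 | 22% |

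The loss of precision shows in the interval for the ratio. The SE of log RR is √[(1−p₁)/(n·p₁) + (1−p₀)/(n·p₀)].

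- s = 1 (28 vs 14 participants): √(0.90/28 + 0.95/14) = 0.316, so the 95% interval is 2.0 ÷ and × 1.86, or 1.08 to 3.72.
- s = 0.5 (14 vs 7 participants): √(0.95/14 + 0.975/7) = 0.455, so the interval is 2.0 ÷ and × 2.44, or 0.82 to 4.88.

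*(b) Old complaints counted as new (muscle pain or weakness).* Observed rate = q + (1 − q) × true rate, where q is the share of participants with a prior complaint that is counted.

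| q | Observed rates | Risk ratio | Difference (points) | Power |
|---|---|---|---|---|
| 0 | 5% vs 10% | 2.0 | 5.0 | 61% |
| 5% | 9.75% vs 14.5% | 1.49 | 4.75 | 41% |
| 10% | 14.5% vs 19.0% | 1.31 | 4.5 | 30% |
| 20% | 24.0% vs 28.0% | 1.17 | 4.0 | 19% |

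This table is an upper bound for each q. It lets every prior complaint into the count, with none removed by the screening record or by the SAP definition.

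The mechanisms differ. Equal under-capture leaves the ratio alone and shrinks the difference and the precision. Counting old complaints pulls the ratio well down and the difference slightly.

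**The case against.** Bruising and bleeding are not left uncollected. Section 8.2.2 takes in events that are volunteered, elicited, or found on examination or laboratory testing, and a blood count is drawn at screening, months 3 and 6, and yearly. Footnote f is worded as an inclusion, not a closed list, and the case report forms are not shown. All of this stands. It rules out the inference that bruising or bleeding is never recorded, or that the trial could not detect an excess. It does not remove the gap between solicited and unsolicited collection, because the visit and phone lists repeat the same conditions without adding bleeding.

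A reader might also infer that muscle pain is under-ascertained, or that pre-existing pain will certainly be counted as an event. The documents support neither. Muscle symptoms fall within the prompted questions at all 16 contacts. The counting rule is left to the SAP, and the screening history, section 9.1, baseline creatine kinase and exclusion 18 give some baseline separation. What remains is that none of these is the same question asked before treatment.

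Finally, the assumed rates have no support in the protocol, warfarin users are excluded at entry, and section 10.9 sets no power target for these outcomes. That is right, and the figures above show only direction and mechanism.

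**Conclusion.** The point holds as a minor one, worth considering. One named key safety outcome lacks a place in the listed safety questions that cover the muscle and gallstone outcomes at 16 contacts by month 48. The muscle questions also have no like-for-like baseline. If the error is equal across arms, as double masking makes plausible, neither gap creates a false signal of harm. Under-capture would leave the risk ratio unchanged while reducing the risk difference and the precision. The missing baseline makes new muscle symptoms harder to identify, and attenuates the comparison only to the extent that old complaints enter the count. How large either effect would be cannot be shown from the protocol. Every power figure above rests on assumed rates, and no planned inference is shown to be wrong.

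**What to change.** 1. Add one bruising/bleeding question to the safety assessment in footnote f and the section 5.3.2 visit lists, and to the phone contacts in section 5.3.5.
2. Put the same symptom questions, including the new one, at the Randomization visit before the first pill (Schedule and section 4.1) for participants not yet randomized, so that new or worsened symptoms can be identified.

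The cost is a short addition to an existing form and call, with no new visit or test. There are two drawbacks. Participants already randomized have no symptom baseline. Section 10.3.2 assumes 259 to 270 enrolled when v6.0 is implemented, leaving 560 − 270 = 290 to 560 − 259 = 301 who could still be asked at that time. The number falls as enrollment proceeds, and section 2.1 expects enrollment to finish within 22 months of v6.0. Bruising ascertainment would also change over calendar time, equally in both arms, so counts before and after the change should be shown separately.
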